#### **4.1.3 Eligibility for the Open-Label Extension**

Participants who have been randomized and who have completed the double-blind treatment period will be eligible to participate in the OLE, provided they do not meet any of the following criteria:

- Discontinued from study treatment during the double-blind treatment period
- Received any other investigational medication during the double-blind treatment period or after the end of double-blind treatment
- Participation in the OLE deemed inappropriate by the investigator (e.g., any serious medical condition or other concerns that preclude the participant's safe participation in the OLE or ability to comply with the required procedures)
- Presence of ARIA-E findings at the Week 116 (or Week 128, if applicable) MRI scan (participants who have ongoing ARIA-E findings at the Week 116 [or Week 128, if applicable] will stay in the double-blind treatment period until the finding is deemed

resolved). For those participants who enroll into the GRADUATE OLE from Week 104, before the double-blind extension took place, eligibility for the OLE would be based on the Week 104 scan.

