## Appendix 1: Schedule of Activities (cont.)

### Table 5: Schedule of Activities (OLE Day 1 to Week 22: Dose Escalation with Q2W Administration) (cont.)

tomography; PK = pharmacokinetic; Q2W = every 2 weeks; QoL-AD = Quality of Life–Alzheimer's Disease; RBR = Research Biosample Repository; RUD-Lite = Resource Utilization in Dementia–Lite; SC = subcutaneous; UV = unscheduled visit; Wk = week; ZCI-AD = Zarit Caregiver Interview–Alzheimer's Disease.

B = before study drug administration; P = participant completion; P&SP= participant and study partner completion; SP=study partner.

Notes: The visit window is  $\pm$  3 days for dosing days and +3 days for OLE non-dosing Day 4. Participants should return to initial planned schedule per randomization for subsequent visits.

- a OLE Day 1 dosing should take place approximately 2 weeks after final efficacy visit has been completed.
- b Visit suitable for home administration of gantenerumab.
- c Accurate recording of the date and time of study drug administration and PK sampling is critical. A PK sample will be obtained as soon as is practical (e.g., at an unscheduled visit) once the site becomes aware of the occurrence or worsening of ARIA-E or of the occurrence of ARIA-H meeting discontinuation criteria
- d Serum chemistry includes AST, ALT, alkaline phosphatase, total protein, total bilirubin, serum albumin, creatine phosphokinase, sodium, potassium, calcium, BUN, and serum creatinine (and creatinine clearance calculated by the central laboratory). At early termination, hemoglobin A1C, glucose, insulin, total cholesterol, HDL, LDL, triglycerides, C-reactive protein, folic acid, vitamin B-12, T4, free T4, and thyroid-stimulating hormone levels will also be assessed and should ideally be collected at least 4 hours after meals.
- e Hematology includes hemoglobin, hematocrit, RBC count (with morphology), WBC counts, platelet, basophil, eosinophil, lymphocyte, monocyte, neutrophil, and WBC–other total counts.
- f A complete physical examination includes an evaluation of the head, eyes, ears, nose, and throat, and the cardiovascular, dermatological, musculoskeletal, respiratory, gastrointestinal, genitourinary, and neurological systems.
- g Limited, symptom-directed physical examinations; changes from baseline abnormalities should be recorded in participant notes.

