Double-blind treatment period: After screening, participants who meet all eligibility criteria will be randomly assigned to one of two arms (active drug or placebo) in a 1:1 ratio. Following baseline assessments, each participant will receive a minimum of 9 subcutaneous (SC) administrations every 4 weeks (Q4W) of study drug (uptitration period), followed by up to 40 administrations every 2 weeks (Q2W) of study drug at target dose in the double-blind treatment period. The last dose of study drug will be administered at Week 114. At the end of the double-blind treatment period, 2 weeks after the last dose, all participants will undergo the final efficacy and safety study visit. Participants who have already completed the double-blind treatment period prior to implementation of Protocol Version 4 will have received up to 34 SC Q2W administrations of study drug during the double-blind treatment period. The last dose will have been administered at Week 102, and their final efficacy and safety visit will be at Week 104.

The Sponsor will emphasize to Investigators the importance of collecting data for the primary endpoint through Week 116, even if participants withdraw from treatment but do not withdraw from the study.

Post-double-blind treatment period: After the final efficacy and safety study visit for the double-blind treatment period, all participants will be asked to come back for the long-term follow-up visits or to continue in the open-label extension (OLE). Participants will either directly enter the separate WN42171 (hereafter referred to as “POSTGRADUATE”) OLE study or enter a parent study OLE period. If entering the parent study OLE period, they will be required to complete the uptitration period (a minimum 36 weeks) following which they will then be able to roll over to the

POSTGRADUATE OLE study. This second option is for participants at sites where POSTGRADUATE is not yet approved when they have reached the end of the double-blind treatment period.

China Enrollment Plan

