5.3.3 Main Analytical Approach for Primary Estimand and Primary Endpoint

Primary study hypothesis

The primary efficacy analysis for this study will test the superiority of the active drug over the placebo at Week 116 with a two-sided test corresponding to the following null hypothesis, H_0 , and alternative hypothesis, H_1 :

$$H_0: \mu_{\text{active}} = \mu_{\text{placebo}}$$

$$H_1: \mu_{\text{active}} \neq \mu_{\text{placebo}}$$

Where μ_{active} and μ_{placebo} are the mean changes from baseline to Week 116 in the CDR-SB score for each arm.

Time Windowing

For the primary endpoint (and in general for clinical efficacy endpoints) the following time windows will be used for analyses (see [Table 4](#)), based on study days. Study days are defined based on days on study since the date of the first dose, with the day of the first dose being study day 1.

Table 4 Time windows for clinical endpoint assessments

| Visit | Target day | Time window (in study days*) |
|----------|------------|--|
| Baseline | 1 | Up to Day 35 |
| Week 24 | 169 | 72, 266 |
| Week 52 | 365 | 267, 448 |
| Week 76 | 533 | 449, 630 |
| Week 104 | 729 | 631, 770 |
| Week 116 | 813 | 771, earliest between 897 or first dose of OLE |

In cases where more than one assessment falls within a time window, the assessment with the date closest to the target day is selected whether it's a scheduled, unscheduled or an early termination visit.

With regards to an ICE of withdrawal from study treatment, an assessment will be regarded as having happened after the ICE of withdrawal from study treatment if it is collected >28 days since the last dose.

General strategy to address the ICEs

For the primary estimand, a treatment policy approach will be used for all SDCR ICEs. In line with the clinical question of interest, the aim is to estimate a treatment effect irrespective of the occurrence of these ICEs. This approach is largely in line with the EMA guideline on the clinical investigation of medicines for the treatment of AD ([EMA 2018](#)).

All NSDCR ICEs will be handled using a hypothetical approach. The aim is to estimate a treatment effect “as if” the ICE had not happened. Post-ICE outcome values compatible with a hypothetical strategy are not directly observable. Consequently, any observed outcome values after NSDCR ICEs will be removed and treated as missing data for analysis purposes.

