5.7.5.3 Visit Windowing

For amyloid PET assessments, due to the long time between scheduled assessments, time windows based on study days, as defined in [Table 7](#), will be used. Study days are defined based on days on study since the date of the first dose, with the day of the first dose being study day 1.

Table 7 Time Windows for Amyloid PET Assessments

| Visit | Target day | Time window |
|----------|------------|--------------|
| Baseline | 1 | Up to day 35 |
| Week 52 | 365 | 281, 449 |
| Week 116 | 813 | 645, 897 |

For Week 116, the time window will cover the week 104 timepoint as well. In case of more than one assessment within a time window, the assessment with the date closest to the target day is selected. For the combined window of Week 104 and 116, the target day is the Week 116 assessment day.

Because of visit windowing, data collected at an early termination visit will be summarized at the corresponding visit as defined by the time window. For participants who have discontinued treatment early, if a PET scan is performed more than 56 days (early termination visit expected 14 days after last dose, followed by time window per protocol for early termination is ± 42 days) after the date of last dose, the PET scan will not be used for the analysis.

The end of a substudy is defined as the date when all participants enrolled in the substudy have:

1. completed the last required amyloid PET scan (Week 116), or
2. completed an early termination scan, or
3. discontinued from the main study.

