Demographics and baseline characteristics (including age, sex, medical history, randomization stratification factors) will be summarized descriptively by treatment arm as assigned for both the CSF-mITT analysis set and the CSF-longitudinal analysis set (see [Table 2](#)) using:

- means, SDs, medians, and ranges for continuous variables
- counts and proportions for categorical variables

Visit Windowing

For CSF assessments time windows based on study days, as defined in [Table 10](#), will be used. Study days are defined based on days on study since the date of the first dose, with the day of the first dose being Study Day 1.

Table 10 Time Windows for CSF Assessments

| Visit | Target study day | Time window |
|----------|------------------|--------------|
| Baseline | 1 | Up to day 35 |
| Week 116 | 813 | 645, 897 |

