5.7.9 Volumetric MRI Analyses

Structural MRI will be analyzed separately for each study (GRADUATE I and GRADUATE II).

Analysis of structural MRI (volumetric MRI) will be based on the MRI-mITT analysis set unless otherwise specified.

Volumetric MRI, for each brain region, will be summarized by treatment group and visit using descriptive statistics for the absolute volume at baseline and percent change from baseline at post-baseline visits.

An MMRM analysis will be used to estimate the mean percent change from baseline to Week 116 (as well Week 48 and 104) in Volumetric MRI for each brain region. The model will include the percent change from baseline in volumetric MRI as the dependent variable, while adjusting for treatment arm (as categorical), visit (as categorical), treatment-by-visit interaction, baseline age, gender (as categorical), APOE ε4 status (as categorical; carrier vs. non-carrier) and disease stage (as categorical). Visit will be treated as the repeated variable within a participant. An unstructured variance-covariance matrix will be applied to model the within-participant errors; in the case of non-convergence, compound symmetry will be used, together with a robust estimator of standard error (“sandwich” estimator).

There will be no data imputation for missing data. However, the MMRM provides unbiased estimates and valid inference in the presence of missing data, under the MAR (missing at random) assumption.

The following brain regions will be considered:

- Whole brain
- Ventricles

- Hippocampus right and left
- Cortical gray matter

Other exploratory analyses based on other brain regions may be reported separately.

Summaries of Treatment Group Comparability

Demographics and baseline characteristics (including age, sex, medical history, randomization stratification factors) will be summarized descriptively by treatment arm as assigned for both the MRI-mITT analysis set and the MRI-longitudinal analysis set (see [Table 2](#)) using:

- means, SDs, medians, and ranges for continuous variables
- counts and proportions for categorical variables

Visit Windowing

For Volumetric MRI assessments time windows based on study days, as defined in [Table 12](#), will be used. Study days are defined based on days on study since the date of the first dose, with the day of the first dose being Study Day 1.

Table 12 Time windows for Volumetric MRI assessments

| Visit | Target study day | Time window |

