|--------------|-------------------------|--------------------|
| Baseline | 1 | Up to Day 35 |
| Week 48 | 337 | 253, 421 |
| Week 104 | 729 | 645, 770 |
| Week 116 | 813 | 771, 897 |

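### The Week 116 window for volumetric MRI is not closed at the first open-label dose, so a Week-104 completer's open-label scan could be analysed as double-blind Week 116 data

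*SAP*

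**What the plan says.** **Clinical endpoints.** SAP Section 5.3.3, Table 4, sets the Week 116 window as "771, earliest between 897 or first dose of OLE". SAP Section 5.6 applies the same principle to safety: double-blind data stop the day before the first OLE dose.

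**Biomarkers.** The five biomarker window tables have no such limit.
- Volumetric MRI (Table 12) and plasma (Table 11): "Week 116 | 813 | 771, 897".
- CSF (Table 10), amyloid PET (Table 7) and tau PET (Table 9): "Week 116 | 813 | 645, 897". The amyloid section explains the wider range: "For Week 116, the time window will cover the week 104 timepoint as well".

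**The clock.** In SAP Section 5.7.9, "Study days are defined based on days on study since the date of the first dose". It does not stop at OLE entry.

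**Who can be affected.** SAP Section 1.2 says of participants who completed before the extension: "The last dose will have been administered at Week 102, and their final efficacy and safety visit will be at Week 104". Protocol Section 4.1.3 allows for them in the extension: "For those participants who enroll into the GRADUATE OLE from Week 104". Protocol Appendix 1, Table 5, adds: "OLE Day 1 dosing should take place approximately 2 weeks after final efficacy visit has been completed". Protocol Section 4.3.2.2 requires a safety MRI before each dose increase in the OLE. The Appendix 1 schedule places the first before the OLE Week 12 dose, at least 7 days ahead of dosing.

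**The concern.** The SAP closes the double-blind period at the first OLE dose in two places and leaves it open in five window tables. For most participants this makes no difference, because the Week 116 visit comes before any open-label dose. It does matter for those who completed at Week 104 and then crossed to open-label treatment, because their Day 813 falls inside the OLE.

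For clinical endpoints, SAP Section 5.3.3 uses these participants as its own example of missing data not tied to an intercurrent event, handled as missing at random. Under Table 12 as written, the same participants could instead have a Week 116 brain volume measured after crossover. Those randomised to placebo would then contribute open-label active-drug data to the placebo-arm Week 116 mean.

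**Working it through.** **1. Reproduce the table limits.** Study day = 7 × week + 1.
- Week 104: 7 × 104 + 1 = 729. Week 116: 7 × 116 + 1 = 813.
- Upper limit: 813 + 84 = 897. Lower limit for MRI and plasma: midpoint (729 + 813) / 2 = 771. Lower limit for CSF and PET: 729 − 84 = 645.
- All agree with the SAP tables.

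**2. Place the OLE visits of a Week-104 completer.**
- OLE Day 1: 729 + 14 = Day 743.
- OLE Week 12 dose: 743 + 84 = Day 827. Pre-dose MRI: by 827 − 7 = Day 820.
- Distance from target: 820 − 813 = 7 days, well inside 771–897.
- If the gap from the final visit to OLE Day 1 is assumed to be 0 to 28 days instead of 14, the scan falls at Day 806 to 834. Any OLE Day 1 from Day 694 (771 − 77) to Day 820 (897 − 77) puts it in the window.
- The double-blind Week 104 scan (Day 729) lies in its own 645–770 window. The OLE Week 24 scan falls by 743 + 168 − 7 = Day 904, outside. The OLE Week 12 scan is therefore the only scheduled scan available as Week 116.

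**3. Exposure by then.** Protocol Table 4 gives former placebo participants active 120 mg at OLE Day 1, Week 4 and Week 8: Days 743, 771 and 799. A scan at Day 820 follows all three.

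**4. Week-116 completers.** OLE Day 1 is about 813 + 14 = Day 827, the OLE Week 12 dose Day 911, and the scan by Day 904, outside the window. It would enter only with a shorter gap or a scan done at least 911 − 897 = 14 days before dosing. These participants also have their own scan at about Day 813.

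**5. The other markers.**
- *Plasma:* the scheduled OLE sample is at OLE Week 24, 743 + 168 = Day 911 (908 with the 3-day visit window), outside 897. It reaches 897 only with a gap of 0 days. Otherwise only early-termination, unscheduled or ARIA-triggered OLE samples can enter.
- *CSF:* the OLE schedule shows CSF only at early termination, decided case by case.
- *PET:* the OLE schedule has no PET row. The 56-day rules are only a partial guard. The visit-windowing rule for amyloid PET is worded for participants who stopped treatment early, which a Week-104 completer did not. The tau rule counts from the last dose without saying last blinded dose. Counted from the last blinded dose (Week 102, Day 715), it ends at 715 + 56 = Day 771; counted from an OLE dose, it gives no protection.

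**6. With the Table 4 limit applied.** For OLE Day 1 at about Day 743, the MRI and plasma Week 116 window is empty, because 743 is before 771. The Week 116 value is missing and the Week 104 value stays where it is. The CSF and PET window becomes Day 645 to about Day 743, which keeps the Week 104 assessment.

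**The case against.** **The SAP is for double-blind analyses.** SAP Section 1 limits its scope to the double-blind period and safety follow-up, sends OLE analyses elsewhere, and leaves dataset detail to Data Analysis Plan modules that are not available here. It is fair to read the omission as a wording gap rather than an intention. But a scope sentence does not select records, and the authors still wrote explicit limits for clinical and safety data.

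**The OLE Week 12 scan is a safety scan.** No text says that its volumes enter the double-blind dataset, and several double-blind safety scans fall outside every post-baseline window in Table 12. This stands as a limit. Against it, Table 12 selects by day and not by purpose of scan, the standard MRI protocol includes a 3D T1-weighted sequence (Protocol Section 4.5.9), and volumetric MRI is an OLE endpoint in all participants (Protocol Table 3). That volumes are derived from this scan remains an inference.

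**The effect is probably small.** Volumetric MRI is exploratory and outside the testing hierarchy. Former active participants stay on 510 mg Q2W. Former placebo participants would have had only three doses at the lowest step. Protocol Section 1.3.1 reports amyloid PET changes at Week 100 of 0.72% with 105 mg against −1.09% with placebo, so no reduction relative to placebo. This supports a modest rating. It does not settle the matter, because those figures concern amyloid signal and not brain volume.

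**Stronger readings.** A reader might infer that OLE samples would displace valid Week 104 CSF and PET values. The documents do not support that. The closest-to-target rule is written for amyloid PET, and the CSF and tau PET sections state no selection rule. No OLE PET scan is scheduled in these documents, and OLE CSF is confined to early termination.

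**Conclusion.** The point holds for volumetric MRI. As written, Table 12 would accept a scheduled open-label scan at about Day 820 as the double-blind Week 116 value of a Week-104 completer who entered the parent-study OLE. For former placebo participants this would tend to contaminate the placebo-arm mean.

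It rests on three assumptions: OLE entry about two weeks after Week 104 (any gap from 0 to 28 days gives the same answer); volumes derived from the OLE Week 12 scan; and no exclusion in the unseen dataset specifications.

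The size cannot be computed. If a fraction f of placebo-arm Week 116 values came from such scans and early open-label treatment shifted them by d on average, a simple mean would move by f × d; neither f nor d is given. The group is narrow. Protocol Version 4 is dated 23 May 2020, so these participants were randomised by about late May 2018, allowing further for implementation lag, and entered the parent-study OLE rather than Study WN42171.

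A reader might conclude that the randomised comparison is broken, or that all biomarkers are affected alike. Neither is shown. The endpoint is exploratory, and CDR-SB and the other clinical endpoints already carry the limit. For Tables 7, 9, 10 and 11 the omission is an inconsistency, with early-termination or off-schedule exposure only for plasma and CSF and none shown for PET.

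**What to change.** - In Table 12, end the Week 116 window at the earlier of Day 897 and the first OLE dose, as Table 4 does.
- Use the same wording in Tables 7, 9, 10 and 11 for consistency.
- State that the last dose in the PET 56-day rules means the last blinded dose.

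Week-104 completers who entered the OLE then have no Week 116 volume. The mixed model in SAP Section 5.7.9 handles this under missing at random, using their earlier scans, in line with the assumption made for their clinical data. The cost is one line per table and one clarifying sentence, with no new data. The price is the loss of some Week 116 values that do not measure the randomised treatment.

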5.8 INTERIM ANALYSES

Details of interim analysis plans are described in a separate interim analysis SAP (iSAP), providing information about a futility interim analysis based on the primary efficacy endpoint CDR-SB.

Other than the futility analysis, there is no plan for an efficacy interim analysis based on the primary endpoint. The primary analysis of the clinical efficacy endpoints will be performed only once, after completion of the efficacy data collection at the end of the double blind part of the study (as described in this SAP) and it will be the only opportunity to formally reject the primary null hypothesis of the trial.

6. SUPPORTING DOCUMENTATION

This document is part of a broader Data Analysis Plan that has several documents, including:

- Graduates studies interim analysis SAP
- Graduates studies Data Analysis Plan Module 2
- Graduates studies Data Analysis Plan Module 3

Appendix 1 Type I Error Control Considerations for Reference-Based Conditional Mean Imputation Combined with the Jackknife for Inference

Introduction

In the GRADUATE trials, hypothetical and treatment policy strategies are applied to Non Study Drug or Condition Related (NSDCR) intercurrent events (ICEs) and Study Drug or Condition Related (SDCR) ICEs, respectively. That is, the clinical interest is in a scenario where SDCR ICEs but not NSDCR ICEs do occur. For estimating the treatment effect, data after NSDCR are assumed to be missing at random (MAR) whereas missing data after SDCR are imputed based on the placebo group in both treatment groups using the copy-increments-in-reference (CIR) imputation method, a specific type of reference-based imputation. We refer to Section 5.3.3 for further details.

The primary analysis of the GRADUATE trials is implemented using conditional mean imputation of missing data combined with the jackknife for inference. This methodology has been described and justified in Wolbers et al. (2022). In this appendix, we provide further details regarding type I error control of the method including additional simulations targeted to the setting of the GRADUATE trials.

Theoretical and published simulation evidence for type I error control

As demonstrated in Section 2.5 of Wolbers et al. (2022), the proposed conditional mean imputation methodology corresponds to a computationally efficient implementation of maximum likelihood multiple imputation. Estimators based on maximum likelihood imputation are asymptotically normal and unbiased if the imputation model and the associated missing data assumptions are correctly specified (Wang and Robins (1998), Robins and Wang [2000]). Moreover, standard error estimates based on resampling methods such as the jackknife or the bootstrap are consistent (Bartlett and Hughes (2020), von Hippel and Bartlett (2021), Wolbers et al. (2022)).

Therefore, large-sample (asymptotic) type I error control is guaranteed if the imputation model and the associated missing data assumptions are correctly specified. This is the case if the following conditions hold:

- All ICEs are correctly identified and classified as NSDCR or SDCR.
- Observed outcome data prior to an ICEs follow a multivariate normal mixed model for repeated measures (MMRM) with an unstructured covariance matrix.
- Missing outcome data prior to an ICE are missing at random (MAR).
- Missing outcome data after NSDCR ICEs compatible with a hypothetical strategy is also MAR.
- Missing outcome data after SDCR ICEs are compatible with the copy-increments-in-reference (CIR) assumption.

In contrast, the commonly used MMRM model requires that all missing data are MAR (Mallinckrodt et al. [2008]). In many settings, a reference-based missing data assumption for SDCR ICEs such as CIR is arguably more plausible and conservative than the MAR assumption of the classical MMRM model.

In order to study type I error control for finite sample sizes, simulation studies are required. A simulation study reported in Wolbers et al. (2022) assessed type I error via simulation (based on 100,000 simulations) for a setting with a relatively low sample size (100 subjects per group), a large proportion of ICEs (34% and 24% in the active and placebo groups, respectively), and a large probability of study drop-out after the occurrence of the ICE of 75%. For standard MAR and all reference-based imputation methods, inference based on conditional mean imputation and jackknifing strictly protected type I error. Simulation results reported in Liu and Pang (2016) for a similar method also found no evidence of type I error inflation for reference-based methods or the MMRM model if the missing data mechanism was correctly specified. These simulation results are also consistent with simulation studies which report that the MMRM model (or an asymptotically equivalent multiple imputation model) provides adequate type I error control if all missing data are MAR (Siddiqui [2011], Lu and Mehrotra [2010]).

In contrast, statistical methods cannot be expected to strictly control type I error if the missing data assumptions are not correctly specified. For example, simulations reported in Liu and Pang (2016) demonstrate type I error inflation for both reference-based methods and the MMRM model if missing data are simulated under certain missing not at random (MNAR) scenarios. Similarly, Mallinckrodt et al. (2004) demonstrated type I inflation of the MMRM model under MNAR scenarios but type I error control of the MMRM model was much closer to nominal values compared to naive approaches to missing data such as the last observation carried forward (LOCF) approach. Whether or not the missing data assumptions is correctly specified is by nature something that cannot be verified

In conclusion, reference-based imputation methods based on conditional mean imputation and jackknifing control type I error if the imputation model and the associated missing data assumptions are correctly specified. Neither reference-based imputation methods nor the MMRM model can guarantee strict type I error control if the missing data assumptions are not correctly specified. Therefore, sensitivity analyses such as tipping point analyses should always be performed to assess the robustness of the results to deviations from the missing data assumptions.

Additional Simulations Targeted to the Setting of the GRADUATE Trials

Methods

We conducted a simulation study to further investigate the type I error control of the reference-based conditional mean imputation combined with the jackknife for inference. The set-up of the simulation study is similar to the simulations reported in [Wolbers et al. \(2022\)](#), but the simulation parameters and the scenarios considered are adapted to the GRADUATE trials. All simulations were for 1:1 randomized placebo-controlled trials with 508 subjects per group and visits at baseline and at 24, 52, 76, 104, and 116 weeks of follow-up. All simulations were performed under the null hypothesis of no difference in mean outcome trajectories between the groups. Scenarios including different probabilities of ICEs in the two groups and/or misclassification of SDCR ICEs as NSDCR ICEs were also included as described below.

Specifically, the other simulation parameters were chosen as follows:

- The mean outcome trajectory in both groups increased linearly from 3.65 to 4.65 during the first 52 weeks from baseline (i.e., an increase of 1 point in the first year), and increased linearly by 1.5 points per year afterwards.
- The variances of the outcomes at baseline and follow-up visits in both groups were: 1.53, 2.08, 2.65, 3.19, 4.26, 4.26.
- The correlation matrix of the baseline and follow-up values in both groups is shown on [Table 1](#).

Table 1 Correlation Matrix

| | Baseline | Week 24 | Week 52 | Week 76 | Week 104 | Week 116 |
|----------|----------|---------|---------|---------|----------|----------|
| Baseline | 1 | 0.72 | 0.60 | 0.54 | 0.52 | 0.52 |
| Week 24 | 0.72 | 1 | 0.72 | 0.60 | 0.54 | 0.54 |
| Week 52 | 0.60 | 0.72 | 1 | 0.72 | 0.60 | 0.60 |
| Week 76 | 0.54 | 0.60 | 0.72 | 1 | 0.72 | 0.72 |
| Week 104 | 0.52 | 0.54 | 0.60 | 0.72 | 1 | 0.85 |
| Week 116 | 0.52 | 0.54 | 0.60 | 0.72 | 0.85 | 1 |

- Two types of intercurrent events were simulated: Study Drug or Condition Related ICEs (SDCR) and Non-Study Drug or Condition Related ICEs (NSDCR).
- Simulation of SDCR ICEs:
 - The probability of an SDCR ICE after each visit was calculated according to a logistic model, which also depended on the observed outcome at that visit.
 - The visit-wise probability of an SDCR ICE for a subject with an observed outcome at that visit of 3.65 was varied across 4 different scenarios as reported in [Table 2](#).
 - The odds of an SDCR ICE further increased by 45% for each 1 point increase in the observed outcome.
 - In the placebo group, an SDCR ICE had no effect on the mean trajectory. In the active group, subjects who experienced an SDCR ICE followed the slope of the mean trajectory from the placebo group from that time point onward (CIR).
 - Study drop-out after the SDCR ICE visit occurred with a probability of 80% leading to missing outcome data from that time point onward.
- Simulation of NSDCR ICEs:
 - The probability of an NSDCR ICEs after each visit was assumed to be independent of the visit and the observed outcome. The specification of these probabilities for each of the 4 scenarios is presented in [Table 2](#).
 - NSDCR ICEs always led to missing outcome data from that time point onward.
- If both SDCR and NSDCR ICEs were simulated to occur for a subject, then it was assumed that only the earlier of them counted. In case both ICEs were simulated to occur at the same time, the event was considered a SDCR ICE. This means that a single subject could experience either a SDCR or a NSDCR ICE, but not both of them.
- Additional missing data unassociated with an ICE was simulated by assuming that a subject missed any visit with a probability of 5%.

Table 2 Specifications of ICEs Probabilities in Each Group for the Four Simulation Scenarios. Only the Parameters that Varied Across Different Scenarios are Presented in this Table.

| | Scenario 1 | Scenario 2 | Scenario 3 | Scenario 4 |
|---|------------|------------|------------|------------|
| Probability of a SDCR ICE after each visit for a subject with outcome equal to 3.65 (PLACEBO) | 2% | 1.5% | 3% | 2.5% |
| Probability of a SDCR ICE after each visit for a subject with outcome equal to 3.65 (ACTIVE) | 2% | 2.5% | 3% | 3.5% |
| Probability of a NSDCR ICE after each visit (PLACEBO) | 2.5% | 2% | 0% | 0% |
| Probability of a NSDCR ICE after each visit (ACTIVE) | 2.5% | 3% | 0% | 0% |

Scenario 1 specifies equal ICE probabilities for the two groups, while Scenario 2 specifies a higher probability of both SDCR and NSDCR events in the active group compared to the placebo group. Scenario 3 simulates only SDCR events, with equal probabilities across the two groups. Scenario 4 also simulates only SDCR events, but with a higher probability in the active group.

Results

The overall probability for a subject to experience either a SDCR or a NSDCR event during the trial under the four scenarios is reported in [Table 3](#). These probabilities were estimated via simulation of a large trial with a sample size of 100'000 subjects per group.

Table 3 Overall Probability for a Subject to Experience Either a SDCR or a NSDCR Event during the Trial under all the Scenarios Considered. Probabilities were Estimated via Simulation of a Large Trial with a Sample Size of 100'000 Subjects Per Group.

| | Scenario 1 | Scenario 2 | Scenario 3 | Scenario 4 |
|------------------------------------|------------|------------|------------|------------|
| Probability of SDCR ICE (PLACEBO) | 21% | 17% | 30% | 27% |
| Probability of SDCR ICE (ACTIVE) | 21% | 24% | 30% | 33% |
| Probability of NSDCR ICE (PLACEBO) | 11% | 9% | 0% | 0% |
| Probability of NSDCR ICE (ACTIVE) | 11% | 12% | 0% | 0% |
| Overall ICE probability (PLACEBO) | 32% | 26% | 30% | 27% |
| Overall ICE probability (ACTIVE) | 32% | 36% | 30% | 33% |

For each scenario considered, we assumed that a given fraction of SDCR ICEs had been misclassified as NSDCR ICEs. That is, we will apply a hypothetical strategy not only to those ICEs that are truly NSDCR, but also to a given fraction of SDCR events. The misclassification rate varied as follows: 0%, 15%, 30%, 45%, where 0% means that there is no misclassification of any SDCR event, while 45% means that 45% of SDCR events will be classified (and handled) as NSDCR events.

Type I error was simulated based on 10'000 simulated trials for each scenario. The respective misclassification rates were then applied to these data before the analysis. The analysis was consistent with the primary analysis of the GRADUATE trial, i.e., conditional mean imputation with jackknife-based inference (as described in [Wolbers et al. \[2022\]](#)) with copy-increments-in-reference (CIR) imputation for missing data after SDCR ICEs.

The simulation results are summarized in [Table 4](#). Simulated type I errors ranged from 4.69% to 5.18% across scenarios and misclassification rates. Simulations based on 10,000 simulated data sets provide a Monte Carlo standard error for type I error estimates of approximately $\pm 0.22\%$. Therefore, these results are fully consistent with strict type I error control at the 5% significance level.

Table 4 Type I Error Rate Estimates for Each of the Scenarios and Misclassification Rates. Simulations are based on 10,000 Simulated Data Sets which Provide a Monte Carlo Standard Error for Type I Error Estimates of Approximately 0.22%.

| Scenario | ICE misclassification rate (from SDCR to NSDCR) | Type I error |
|------------|---|--------------|
| Scenario 1 | 0% | 4.95% |
| | 15% | 4.84% |
| | 30% | 4.97% |
| | 45% | 4.83% |
| Scenario 2 | 0% | 5.11% |
| | 15% | 5.00% |
| | 30% | 5.18% |
| | 45% | 5.13% |
| Scenario 3 | 0% | 4.98% |
| | 15% | 4.81% |
| | 30% | 4.82% |
| | 45% | 4.69% |
| Scenario 4 | 0% | 4.73% |
| | 15% | 4.78% |
| | 30% | 5.00% |
| | 45% | 5.01% |

Conclusion

The primary analysis described in this SAP is based on the method described in [Wolbers et al. \(2022\)](#). This publication describes and justifies the method in detail and provides theoretical and simulation support that it controls type I error.

Clarification and details on the theoretical argument were provided and additional simulations were conducted. These simulations explored plausible scenarios calibrated to the GRADUATE studies. They also assessed the impact of ICE misclassification.

Based on this body of evidence, the proposed method for primary analysis (using conditional mean imputation of missing data combined with the jackknife for inference) adequately controls type I error.

